Grade 3 or 4 tumor lysis syndrome	
 • Treatment may continue for Grade 3 provided that there is no significant organ dysfunction that necessitates pausing therapy. Treatment may be interrupted so that supportive care can be initiated, with treatment resuming at the discretion of the investigator. Treatment should resume at the start of the next cycle. • Grade 4 should require treatment interruption until resolution of tumor lysis syndrome. If treatment for a cycle is interrupted due to tumor lysis syndrome and cannot be resumed, treatment can be omitted for the rest of the current cycle and resumed at the same time point in the next cycle in conjunction with prophylactic therapy.
Grade 3 Infusion related reaction (IRR), second episode	
 • Discontinue obinutuzumab or polatuzumab vedotin permanently. • If IRR is attributed to obinutuzumab, continue polatuzumab vedotin • If IRR is attributed to polatuzumab vedotin, continue obinutuzumab
Anaphylaxis or Grade 4 IRR	
 • Discontinue obinutuzumab or polatuzumab vedotin permanently. • If anaphylaxis is attributed to obinutuzumab, continue polatuzumab vedotin • If anaphylaxis is attributed to polatuzumab vedotin, continue obinutuzumab
Grade 3 or 4 non-hematologic toxicity not otherwise specified (excluding nausea, vomiting, and diarrhea)	
 • Consider delaying all study treatment for a maximum of 14 days. • First occurrence: Based on the nature of the toxicity, decrease polatuzumab vedotin dose for the next cycle. • Second and subsequent recurrence: Based on the nature of the toxicity and if the toxicity is manageable and resolving within 14 days of the date of the next scheduled cycle, continue treatment. If the toxicity is not manageable or does not resolve, discontinue of suspect study treatment permanently.

^a Based on laboratory results obtained within 72 hours before study treatment administration on Day 1 of each cycle.

Infusion-Related Reactions and Anaphylaxis

Medications including epinephrine for subcutaneous injections, corticosteroids, diphenhydramine hydrochloride for IV injection, and resuscitation equipment should be available for immediate use. Recommended management of infusion-related symptoms for Obinutuzumab is summarized in Table 6, but final decision for acute management is at the discretion of the investigator. Future administration of the study agent that caused the reaction should be dictated by the guidance in Table 6.

Table 6: Management of infusion related reactions

Infusion-related symptoms	Guidance
Grade 1-2	Slow or hold infusion. Give supportive treatment. Upon symptom resolution, may resume infusion-rate escalation at the investigator's discretion. Note: For Grade 2 wheezing or urticaria, patient must be premedicated for any subsequent doses
Grade 3	Discontinue infusion. Give supportive treatment. Upon symptom resolution, may resume infusion-rate escalation, at investigator discretion. Note: If the same adverse event recurs as Grade 3-4 despite adequate pre-medication, treatment for the attributable drug must be permanently discontinued. Note: For Grade 3 hypotension or fever, patient must be premedicated before re-treatment. If symptoms recur at same grade or higher, then patient must be permanently discontinued from study drug. Note: If patient has Grade 3 wheezing, bronchospasm, or generalized urticaria at first occurrence, patient must be permanently discontinued from study drug.
Grade 4	Discontinue infusion immediately, treat symptoms aggressively, and permanently discontinue attributable study drug.

Table 7: Premedication for Obinutuzumab and Polatuzumab Vedotin

Timepoint	Patients who Require Premedication	Premedication	Administration
Cycle 9, Day 1	All patients	Corticosteroid ^a	Complete \geq 1 hour prior to obinutuzumab administration
		Antihistamine drug ^b and analgesic/anti-pyretic ^c	Administer \geq 30 minutes prior to obinutuzumab administration. Antihistamine may be re-administered administration of any polatuzumab vedotin
Cycle 9, Day 8, 15	Patients with no IRR during the previous infusion	Corticosteroid ^a	Complete \geq 1 hour prior to obinutuzumab administration
		Antihistamine drug ^b and analgesic/anti-pyretic ^c	Administer \geq 30 minutes prior to obinutuzumab administration
	Patients with Grade 1 or 2 IRR during the previous infusion	Corticosteroid ^a	Complete \geq 1 hour prior to obinutuzumab administration
		Antihistamine drug ^b and analgesic/anti-pyretic ^c	Administer \geq 30 minutes prior to obinutuzumab administration
	Patients with Grade 3 IRR, wheezing, urticaria, or other symptoms of anaphylaxis during the previous infusion OR Patients with bulky disease	Corticosteroid ^a	Complete \geq 1 hour prior to obinutuzumab administration
		Antihistamine drug ^b and analgesic/anti-pyretic ^c	Administer \geq 30 minutes prior to obinutuzumab administration
Cycle 10 and beyond, Day 1	Patients with no IRR during the previous infusion	Corticosteroid ^a	Complete \geq 1 hour prior to obinutuzumab administration
		Antihistamine drug ^b and analgesic/anti-pyretic ^c	Administer \geq 30 minutes prior to obinutuzumab administration. Antihistamine may be omitted on Day 1 at investigator's discretion.
	Patients with Grade 1 or 2 IRR during the previous infusion	Corticosteroid ^a	Complete \geq 1 hour prior to obinutuzumab administration
		Antihistamine drug ^b and analgesic/anti-pyretic ^c	Administer \geq 30 minutes prior to obinutuzumab administration. Antihistamine may be re-administered administration of any polatuzumab vedotin

			administration of any polatuzumab
	Patients with Grade 3 IRR, wheezing, urticaria, or other symptoms of anaphylaxis during the previous infusion OR Patients with bulky disease	Corticosteroid ^a	Complete \geq 1 hour prior to obinutuzumab
		Antihistamine drug ^b and analgesic/anti-pyretic ^c	Administer \geq 30 minutes prior to administration of any polatuzumab may be re-administered administration of any polatuzumab

^a Methylprednisolone 80 mg or dexamethasone 20 mg or equivalent

^b For example, diphenhydramine 25-50 mg IV/PO or equivalent

^c For example, acetaminophen 650-1000 mg or equivalent

All obinutuzumab infusions should be administered to patients after premedication per above table. Additional premedication beyond what is outlined above (eg. Famotidine) may be administered at the discretion of the investigator.

Infection Prophylaxis

Anti-infective prophylaxis for viral, fungal, bacterial, or Pneumocystis infections should be instituted per institutional practice or investigator preference based on individual patient risk factors. Patients at risk for reactivation of Hepatitis B should receive prophylactic antiviral medications per institutional standard of care.

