Subjects who must permanently discontinue mosunetuzumab monotherapy due to toxicity should have a response assessment with positron emission tomography (PET)/CT as soon as is clinically feasible and be evaluated for consideration of treatment in Part B as outlined below. These subjects would then be realigned to cycle 9 day 1 provided at least 21 days \pm 2 days have passed since the last mosunetuzumab injection

Subjects will undergo a computed tomography (CT) between cycle 4 day 1 and cycle 5 day 1. Those with at least stable disease (SD) or better by Lugano²³ criteria will proceed with treatment for cycles 5-8. Subjects with progressive disease (PD) at this timepoint may proceed with cycles 5-8 if the investigator assesses that the subject is deriving clinical benefit from the study medication (e.g. pseudoprogression). If there is no clinical benefit to this medication seen in patients with PD, subjects should receive additional therapy outside of the protocol.

Imaging with a PET/CT will be performed between cycle 8 day 1 and cycle 9 day 1. Subjects in a complete remission (CR) will not receive any further study therapy and will be observed in long term follow up. For this response assessment, a Deauville score will be assigned by the clinical radiology read. If the sub-investigator or principal investigator disagrees with the Deauville score assigned, another nuclear medicine physician will adjudicate the results.

All other subjects who do not achieve a CR may proceed with Part B of study treatment. Those with progressive disease (PD) may proceed with Part B only if they are deriving clinical benefit from the treatment (e.g., pseudoprogression, mixed response overall reduction in tumor) after discussion with the Principal Investigator.

Mosunetuzumab Dose Modifications/Toxicity Management

Administration of mosunetuzumab will be performed in a clinical setting with immediate access to a code team staff who are trained to monitor for and respond to medical emergencies. Additional management may take place after transfer to the University of Washington Medical Center, where there is access to neurology and nephrology consultation services in the event of cytokine release syndrome and tumor lysis syndrome, respectively.

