The recommended management of CRS is listed in Appendix 14.5 and recommended management of hemophagocytic lymphohistiocytosis (HLH) is listed in Appendix 14.6. Details and recommended management of tumor lysis syndrome are listed in section 14.7 and 14.8.

Because TLS (Appendix 14.7 and 14.8) represents a pharmacodynamic effect of mosunetuzumab anti-tumor activity that may result in clinical benefit, patients who experience Grade 4 TLS may be considered for continued study treatment. In order to be considered for subsequent study treatment, all toxicities and laboratory abnormalities

related to TLS resolved within 2 weeks. The decision to continue study treatment should only be made after consultation with the study investigator and approval by the Principal Investigator. Any exceptions must have the approval of the principal investigator.

Patients who experience a treatment-related grade 3 non-hematologic adverse event or serious adverse event not mentioned above will be allowed to delay mosunetuzumab dosing for up to 2 weeks in order to recover from the toxicity. Additional delays must be discussed with the principal investigator prior to considerations of resuming study therapy.

In general, patients receiving mosunetuzumab who experience a Grade 4 non-hematological treatment-related adverse event should discontinue all study treatment and may not be re-treated. Subjects who discontinue mosunetuzumab due to toxicity may proceed to Part B at investigator discretion, but should have a repeat response assessment prior to initiating therapy in Part B.

For those non-hematologic adverse events that are not considered by the investigator to be attributable to another clearly identifiable cause, (e.g., documented disease progression, concomitant medication, or pre-existing medical condition), and thought to be attributable to mosunetuzumab, patients may continue to receive additional doses of mosunetuzumab, provided that the toxicity has resolved to Grade ≤ 1 . Corticosteroids may be used as indicated for the management of non-CRS adverse events related to mosunetuzumab. One can consider resuming mosunetuzumab after resolution of the toxicity to Grade ≤ 1 and steroid dosing of prednisone ≤ 10 mg PO daily or less

- For decreased lab values, the abnormality should have resolved to the lower limit of Grade ≤ 1 , or return to $\geq 80\%$ of the baseline value, whichever is lower.

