7.1.6.3 End of Treatment/Off Study Visit

At the completion of Part A, subjects will undergo a response assessment and clinic visit at the time of a possible cycle 9 day 1. For subjects with a CR, the visit that day will be called an end of treatment visit with labs/assessments outlined in section 6.1. An additional off-study visit 4-6 weeks after last dose of study drug will be required as well.

For subjects who do not achieve a CR in Part A and are eligible to proceed to Part B, Cycle 9 Day 1 will occur instead of an end of treatment visit. An off study visit alone will occur in lieu of an end of treatment visit 4-6 weeks after the last dose of study therapy. This visit will include review of tumor imaging (FDG PET-CT) as well as medical history, physical exam, and laboratory evaluations required for determination of remission status. Patients who come

off study early due to suspected progression or toxicity should have a clinic visit and tumor imaging as soon as it can be safely performed. Subjects who discontinue mosunetuzumab due to toxicity may undergo a response assessment, and if not in a CR, may proceed with part B. Remission status is to be determined according to 2014 Criteria (“The Lugano Classification”)²³ as in Appendix 14.3.

For patients with equivocal post-induction imaging or clinical findings, in whom remission status cannot be clearly ascertained, further workup as per clinical standard of care including tumor biopsy or repeat imaging should be undertaken to confirm remission status (PR or CR) prior to proceeding onto the Follow-Up Period

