^a Immune-related event should be considered when concurrent clinical and laboratory manifestations of CRS or HLH are present, or in instances where no alternative etiology (e.g., viral, neoplastic) can account for observed LFT abnormalities.

^b Resumption of mosunetuzumab may be considered in patients who are deriving benefit and who have fully recovered from the immune-related event. Patients may resume dosing with mosunetuzumab only after documented approval by the Principal Investigator.

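### After a grade 4 non-hematologic event on mosunetuzumab, Section 5.3 ends all study treatment, while other text allows Part B or further mosunetuzumab, and no precedence is stated

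*Combined protocol and SAP*

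**What the plan says.** The restrictive rule is in Section 5.3, under mosunetuzumab dose modifications. It begins "In general, patients receiving mosunetuzumab who experience a Grade 4 non-hematological treatment-related adverse event" and continues "should discontinue all study treatment and may not be re-treated".

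The sentence directly after it reads "Subjects who discontinue mosunetuzumab due to toxicity may proceed to Part B at investigator discretion", subject to a repeat response assessment. Earlier in Section 5.3, the Part A text opens "Subjects who must permanently discontinue mosunetuzumab monotherapy due to toxicity should have a response assessment" and adds that these subjects should "be evaluated for consideration of treatment in Part B as outlined below". Section 7.1.6.3 returns to the subject: "Subjects who discontinue mosunetuzumab due to toxicity may undergo a response assessment, and if not in a CR, may proceed with part B".

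On mosunetuzumab itself, the next paragraph of Section 5.3 deals with non-hematologic events thought to be due to the drug. It says that "patients may continue to receive additional doses of mosunetuzumab, provided that the toxicity has resolved to Grade" 1 or lower. In Appendix 14.13, the grade 4 row of Table 22 stops mosunetuzumab permanently, but its footnote contemplates resumption: "Patients may resume dosing with mosunetuzumab only after documented approval by the Principal Investigator". Appendices 14.10 and 14.15 carry further grade 4 entries, set out in the working.

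**The concern.** Section 5.3 itself describes Part B as study treatment, so an instruction to stop all study treatment covers Part B as well as mosunetuzumab. Read literally, the grade 4 sentence closes both routes, while the sentences around it and the appendices open them. A protocol needs one answer for a patient who has just had a life-threatening drug-related event, and here it gives several.

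There is also a possible link to the primary endpoint, which is CR as best response by the end of therapy. Part B is the protocol's route to CR for patients who have not reached it on mosunetuzumab. Whether a grade 4 patient may enter Part B can therefore decide whether that patient still has a chance of counting as a response.

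**Working it through.** This point is textual and disputes none of the plan's figures, so the check is a side-by-side reading.

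| Place | Applies to | Limit on grade | Consequence | Who decides |
|---|---|---|---|---|
| 5.3, grade 4 sentence | Related non-hematologic event on mosunetuzumab | Grade 4 | All study treatment ends; no re-treatment; worded as a default | Not named |
| 5.3, next sentence | Mosunetuzumab stopped for toxicity | None | Part B possible | Investigator |
| 5.3, Part A text | Mosunetuzumab permanently stopped for toxicity | None | PET/CT, evaluation for Part B, realignment to cycle 9 day 1 | Not named |
| 7.1.6.3 | Mosunetuzumab stopped for toxicity, not in CR | None | Part B possible | Not named |
| 5.3, next paragraph | Non-hematologic event attributed to mosunetuzumab | None on original grade | Further mosunetuzumab after recovery to Grade 1 or lower | Not named |
| 14.13, Table 22 and footnote b | AST/ALT elevation | Grade 4 row | Permanent stop, but resumption may be considered after full recovery if the patient is benefiting | Principal Investigator, documented |
| 14.15, Table 23 | Injection-site reaction | Grade 4 row | SC stopped; IV mosunetuzumab may be considered | After discussion with Principal Investigator |
| 14.10, Tables 17 and 19 | Tumor flare in the oropharynx, or outside it and the mediastinum | Grade 4 entries | Hold until recovery; permanent stop only to be considered | After discussion with Principal Investigator |
| 5.3, tumor lysis text | Tumor lysis syndrome | Grade 4 | Continued treatment may be considered if resolved within 2 weeks | Principal Investigator approval |

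Four things follow.

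1. **Part B entry.** The first row excludes it after a grade 4 event. The second and fourth rows permit it without reference to grade. The third row is weaker, because it only sends the subject for evaluation under later text. It does, however, concern patients who must stop permanently, a group that includes those with a grade 4 event.
2. **Mosunetuzumab resumption.** The first row excludes it. The fifth row permits it after recovery, whatever the starting grade. The AST/ALT footnote, the injection-site row and the flare entries permit it specifically at grade 4.
3. **A second conflict inside the injection-site row.** It offers IV mosunetuzumab, whereas Appendix 14.16 says that intravenous formulations are not used in this study.
4. **Precedence.** Section 5.3 calls several of the appendices additional guidance but does not say whether they override the body text. Tumor lysis is the only grade 4 event written as an exception in the body, with both a recovery condition and an approver.

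Take, as an example, a patient not in CR who has a related grade 4 ALT elevation in cycle 3. The grade 4 sentence ends all study treatment. The following sentence allows Part B at the investigator's discretion. The liver footnote allows a return to mosunetuzumab with documented Principal Investigator approval. These are three different courses for one patient, each with support in the current text.

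**The case against.** The strongest defense is that the text can be read coherently. The grade 4 sentence is a default, as its opening words show. The Part B sentence covers the wider group who stop mosunetuzumab for any toxicity, and it has work to do below grade 4, for example after a recurrent Grade 3 neurologic event. The appendix entries are then event-specific exceptions, several of them requiring contact with or approval by the Principal Investigator. The Part A text defers to what follows, and Section 7.1.6.3 is a visit section that says only that subjects may proceed.

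Much of this is fair, and it may be what was meant. But the protocol does not say it. The Part B sentence directly follows the grade 4 rule and carries no limit. The default names neither its exceptions nor who grants them. The lower-grade reading would also leave the grade 4 appendix entries unexplained.

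Stronger readings are tempting but not supported:

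- **That sites will treat and score these patients differently.** The documents describe one institutional consortium, some of these decisions go through the Principal Investigator, and response has one standard (Lugano) and one evaluability rule. Investigators may differ in treatment. No conflict in scoring is shown.
- **That the chance of trial success shifts by a stated amount.** The plan's probability of 0.53 for 34 or more CRs in 42 at a true rate of 80% reproduces: P(X ≥ 34 | 42, 0.80) = 0.531. Fixing one patient's outcome gives P(X ≥ 34 | 41, 0.80) = 0.407 if that patient is not a CR and P(X ≥ 33 | 41, 0.80) = 0.562 if the patient is. That shows how much any one patient matters, and does not measure this conflict.
- **That about 4 of 42 patients are affected.** Section 8.0 expects grade 4 non-hematologic toxicity in under 10%, and 0.10 × 42 = 4.2. That expectation is not confined to Part A and includes patients who may already be in CR. Only Part A grade 4 patients not yet in CR are relevant here, and their number is not given.

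**Conclusion.** The inconsistency is real, lies in current operative safety text, and should be corrected. It concerns both Part B entry and mosunetuzumab resumption after a grade 4 non-hematologic related event. Neither the hedge at the start of the rule nor the lower-grade reading settles it, because tumor lysis is the only written exception and no order of precedence is stated.

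The conclusion rests on two readings: that stopping all study treatment includes Part B, and that a permission with no grade limit reaches grade 4. The effect on the primary endpoint is an inference from the endpoint definition. It is possible but cannot be sized from the documents, and no success probability should be attached to it.

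**What to change.** Reconcile the following in the next amendment:

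- Section 5.3: the Part A text on permanent discontinuation, the grade 4 sentence, the Part B sentence after it, and the paragraph on further doses after recovery.
- Section 7.1.6.3: the sentence on Part B after toxicity.
- Appendix 14.10: the grade 4 tumor flare entries.
- Appendix 14.13: the grade 4 row of Table 22 and footnote b.
- Appendix 14.15: the grade 4 row of Table 23, together with the Appendix 14.16 statement on IV formulations.

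One statement should say whether the grade 4 rule limits Part B entry and mosunetuzumab resumption, which event-specific appendix entries are exceptions to it, and who approves each. The other places should then refer to that statement. Which rule applies is for the clinical team to decide. The cost is amendment wording; the sample size, endpoint definition and success criterion need not change.

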5.3.1 Timing of Dose Administration

Trial treatment should be generally be administered as outlined in section 5.2 starting on the day of each cycle as outlined in the Trial Flow Chart (Section 6.1). Missed doses of polatuzumab vedotin or obinutuzumab will not be made up.

The polatuzumab vedotin and obinutuzimab prescribing information contains specific instructions for polatuzumab vedotin reconstitution, preparation of the infusion fluid, and administration. The mosunetuzumab investigator brochure and appendix 14.15 will have the same information.

5.3.2 Trial Blinding/Masking

This is an open-label, single arm prospective trial; therefore, the investigator and subject will know the treatment administered.

5.4 Concomitant Medications/Vaccinations (allowed & prohibited)

Medications or vaccinations specifically prohibited in the exclusion criteria are not allowed during the ongoing trial. If there is a clinical indication for one of these or other medications or vaccinations specifically prohibited during the trial, discontinuation from trial therapy or vaccination may be required. The final decision on any supportive therapy or vaccination rests with the investigator and/or the subject's primary physician. However, the decision to continue the subject on trial therapy or vaccination schedule requires the mutual agreement of the Investigator and the subject.

